2.11 Patient reported outcomes

The analysis for the patient reported outcome ECog, along with the Informant (study partner) version, is described within the secondary efficacy variables [Section 2.7](#), and eCSSRS is described in the safety analysis [Section 2.8](#).

2.12 Biomarkers

The biomarkers are described in secondary variables [Section 2.7](#).

The table content is redacted with black boxes.

2.14 Interim analysis

Due to early termination of the studies, the planned IA for CNP520 will not be performed.

3 Sample size calculation

A total of up to 2000 participants will be randomized into the study, with a sample size of 800 for the selected dose of CNP520 and placebo, respectively, thereby achieving a 1:1 ratio for the selected CNP520 dose vs placebo. Sample size calculations were mainly based on reaching a target power of 80% for the test of the elementary hypothesis on the TTE endpoint for the selected dose of CNP520 vs placebo.

Type I Error Rate and Power

The overall significance level will be $\alpha=5\%$ (rate of any false positive decision, i.e., at least one Null-Hypothesis is rejected although all were true). The overall α of 5% will be split between the two primary hypotheses on the two primary endpoints as follows: An alpha of 4% will be chosen to test the hypothesis H₀₁ on the time to first diagnosis of MCI or dementia due to AD; an alpha of 1% will be chosen to test the hypothesis H₀₂ on the APCC score.

A small portion (0.004% and 0.001%, respectively) of the error rates will be spent in a Bonferroni split to account for multiplicity due to the IA on primary endpoints. Since the portion will be very small, this has been ignored for power calculations.

Sample size calculations were mainly driven by power considerations for the primary endpoint time to first diagnosis of MCI or dementia due to AD, based on the planned recruitment time of two years and variable observation period of five to seven years. The power, i.e., the probability to detect a true difference between treatment arms, was set to be at least 80% for this analysis.

The power for the primary analysis does not account for the potential and non-negligible inflation of the type II error due to futility analyses using biomarkers and the primary efficacy endpoints. On the other hand, the potential inflation of the type II error due to the adaptive design is expected to be minimal and hence, has been ignored for the calculations of sample size.

Simulations

The sample size of the trial has been calculated based on simulations. Further details are described in the Sample Size documentation.

Sample Size Calculation based on the Primary Endpoint Time to MCI / Dementia due to AD

The sample size calculation for the TTE endpoint, i.e., for time to first diagnosis of MCI due to AD or dementia due to AD has been based on the following assumptions:

two years accrual period,

five to seven years observation period,

30% of participants experiencing an event in the control group in 60 months observation period,

a hazard ratio of 0.75 in favor of the active treatment arm,

30% drop-out rate over 60 months (corresponding to a yearly drop-out rate of about 6.9%),
 $\alpha = 4\%$, two-sided test.

Power has been investigated for the comparison of the CNP520 high dose versus placebo using a log-rank test under Lakatos approximation. Based on the above-mentioned assumptions, a sample size of 1600 participants (800 participants in the selected CNP520 dose group and placebo, respectively) need to be randomized to achieve at least 80% power. The targeted number of events required to be observed in the active treatment arm is 180 and that placebo group is 228 adding up to a total of 408 target events for the comparison of the primary active arm versus placebo. Assuming the same underlying event rate of 22.5% in the active treatment arms, the targeted number of events in the secondary active arm is calculated as 22.5% of the total number of participants in the arm (i.e. 90 events). Supposing therefore that no adaptation occurred (i.e. 2000 participants randomized), the overall targeted number of events is 498 (= 228 + 180 + 90). The power estimation using the log-rank test provides a conservative estimate and should thus be interpreted as the lower limit of power.

In the simulation setting, the trial data were simulated using models which included certain prognostic factors. This enabled the investigation of different population assumptions and allowed each subject to have its own TTE distribution depending on baseline characteristics. The power estimates based on the adjusted Cox PH model hence were overly optimistic and should be interpreted as the upper limit of power which may only be reached in a best case scenario. Power for the TTE endpoints reached 89% and more in simulations depending on the underlying assumptions on the population.

The above calculation was done using the commercial software PASS 2008.

Power calculations based on the primary endpoint APCC

Power considerations for the APCC have been based on the MMRM model generated from the simulated trials and on standard power calculation based on a t-test. The following assumptions for the power calculations based on the change from baseline to Week 260_(M 60) in APCC were used:

- Statistical test used: t-test (standard) and MMRM (simulations),
- 30% drop-out rate over five years,
- Target power of 80%,
- $\alpha = 1\%$, two-sided test.

The sample size of $n = 800$ participants in the selected CNP520 dose arm and placebo, respectively, is sufficient to detect an effect size of 0.20 with 80% power. Results from simulations indicate that using a longitudinal model and adjusting for prognostic factors will increase power to detect an effect size of 0.20.

Power calculations for APCC using the two-sided t-test have been performed with nQuery Advisor 7.0.

Overall power

The overall power to detect a true treatment effect in at least one of the two endpoints is higher as compared to the power for the single endpoints. The difference in power between the dual and single endpoints is largest when the endpoints are independent and will be small when the endpoints are strongly positively correlated.

4 Change to protocol specified analyses

SAF definition (defined in [Section 2.2](#)) is different from the protocol defined SAF definition.

An additional analysis set, mSAF, has been defined.

The following analysis were defined in the protocol but will not be performed due to early termination of the study:

- Primary analysis for both the primary endpoints
- Sensitivity to the primary analysis
- Supportive analysis to primary endpoints
- MMRM analysis to key secondary endpoint
- MMRM analysis to secondary efficacy endpoints

■ [REDACTED]

The following analysis were not defined in the protocol but will be added:

- All the efficacy analysis (except worsening in cognition and reversibility) will be performed on the SAF
- Worsening in cognition and reversibility as efficacy analysis using mSAF

5 Appendix

5.1 Imputation rules

5.1.1 Study drug

If study treatment end date is missing, then treatment epoch completion date will be considered the last dose date, the rule will be provided in Programming Dataset Specification (PDS) document in details.

5.1.2 AE date imputation

Rules for imputing AE end date or start date will be provided in Programming Dataset Specification (PDS) document in details.

5.1.3 Concomitant medication date imputation

Rules for imputing the CM end date or start date will be provided in Programming Dataset Specification (PDS) document in details.

5.1.3.1 Prior therapies date imputation

Not Applicable.

5.1.3.2 Post therapies date imputation

Rules for imputing the post non-drug therapies end date or start date will be provided in Programming Dataset Specification (PDS) document in details.

5.1.3.3 Other imputations

5.1.3.3.1 Missing values from the same latent variable

For subtests that contribute to the same latent construct variable ([Table 5-1](#)), the following rule for missing subtests will be applied: When less than or equal to 50% of the related subtests within a constructed latent variable is missing, these missing subtests will be imputed from the remaining subtests contributing to its latent variable, standardized so that each subtest contributes the same weight to the construct as it would have if measured.

Table 5-1 Latent construct variables and their corresponding subtests

Latent construct variable	Subtests
Immediate Memory Index score	List Learning and Story Memory
Visuospatial/Constructional Index Score	Figure Copy and Line Orientation
Language Index Score	Semantic Fluency and Picture Naming
Attention Index Score	Coding and Digital Span
Delayed Memory Index Score	List Recall, Story Recall, Figure Recall and List Recognition

Latent construct variable	Subtests
Raven's matrices contributing to APCC	A2, A4, A8, B1-B6

This is done by calculating the total subscale-weight adjusted observed subtests (*i*), divided by the maximum weight-adjusted values possible for the observed subtests (*i*). This will provide the proportion to apply to the missing subtest (*j*) maximum possible value in order to obtain its imputed value as follows:

$$\text{missing subtest}_j = \frac{\sum_{i=1}^n (\text{weight}_i \times \text{observed subtest}_i)}{\sum_{i=1}^n (\text{weight}_i \times \text{observed subtest max}_i)} \times \text{missing subtest}_j \text{ max.}$$

Missing subtests that could not borrow information from observed related subtests and construct variable values which could not be calculated from their underlying observed/imputed values will be regarded as MAR and will not be imputed.

5.2 AEs coding/grading

The MedDRA version which will be available at the time of database lock, will be used for the coding purpose of the adverse events.

5.3 Laboratory parameters derivations

Table 5-2 Liver Event and Laboratory Trigger Definitions

	Definition/ threshold
LIVER LABORATORY TRIGGERS	3×ULN < ALT / AST ≤ 5×ULN 1.5×ULN < TBL ≤ 2×ULN
LIVER EVENTS	ALT or AST > 5 × ULN ALP > 2×ULN (in the absence of known bone pathology) TBL > 2×ULN (in the absence of known Gilbert syndrome) ALT or AST > 3×ULN and INR > 1.5 Potential Hy's Law cases (defined as ALT or AST > 3×ULN and TBL > 2×ULN [mainly conjugated fraction] without notable increase in ALP to > 2×ULN) Any clinical event of jaundice (or equivalent term) ALT or AST > 3×ULN accompanied# by (general) malaise, fatigue, abdominal pain, nausea, or vomiting, or rash with eosinophilia Any adverse event potentially indicative of a liver toxicity *

*These events cover the following: hepatic failure, fibrosis and cirrhosis, and other liver damagerelated conditions; the non-infectious hepatitis; the benign, malignant and unspecified liver neoplasms

#Consider these adverse events in a window from 30 days before the liver event criteria (ALT or AST > 3×ULN) to 30 days after the liver event criteria (ALT or AST > 3×ULN).

ALP = alkaline phosphatase; ALT = Alanine aminotransferase; AST = Aspartate aminotransferase TBL: total bilirubin; ULN: upper limit of normal

Table 5-3 Specific renal alert criteria and actions

	Definition/ threshold
Serum event	Serum creatinine increase 25 – 49% compared to baseline Acute Kidney Injury: Serum creatinine increase \geq 50% compared to baseline
Urine event	New dipstick proteinuria \geq 1+ Albumin- or Protein-creatinine ratio increase \geq 2-fold ACR \geq 30 mg/g or \geq 3 mg/mmol; PCR \geq 150 mg/g or $>$ 15 mg/mmol New dipstick glycosuria \geq 1+ not due to diabetes New dipstick hematuria \geq 1+ not due to trauma*

ACR = Albumin-creatinine ratio; PCR = Protein-creatinine ratio

*Consider adverse event (injury) in a window from 30 days before the hematuria criteria.

5.4 Statistical models

SAS codes for all statistical methodology described in this section will be included as programming note in TFL Shells.

5.4.1 Primary analysis

Kaplan Meier approach for TTE

The Kaplan-Meier estimates of the survival functions for each treatment will be plotted. The plot will include the number of participants at risk for each treatment group at pre-specified timepoints. Median time to event and quartiles including 95% confidence intervals, if estimable, will be provided for each treatment group using the SAS procedure LIFETEST. The confidence intervals will be based on log-log transformation. For each treatment group and time interval: participants at risk, participants with event, participants with event divided by participants at risk, cumulative participants with event and cumulative event probability including 95% confidence interval will be provided.

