Withdrawal of study consent (WoC)	Withdrawal of consent from the study occurs only when the participant does not want to continue in the study any longer, and does not allow any further collection of personal data

Amendment 03 (7-Jan-2020)

Amendment rationale

This amendment documents, for completeness, the **changes regarding follow-up of participants after early termination of the study according to the Investigators Notifications distributed between July-2019 and December-2019.**

The changes related to discontinuation of treatment with CNP520 were already formally communicated via an Urgent Safety Measure (USM) dated 11-Jul-2019 and two subsequent Follow-up Notifications (dated 1-Aug-2019 and 12-Dec-2019) summarized below.

The USM (11-Jul-2019) was triggered by an unexpected, mild, early worsening that was observed in some measures of cognition in the active treatment arms following the assessment of unblinded data of CNP520 by the independent Data Monitoring Committee (DMC), during a planned data review on 26 June 2019. This finding led the Sponsors to discontinue assessment of CNP520 in the two Phase 2/3 studies in the Generation Program in July 2019. Additionally, volumetric MRI (whole brain and hippocampal volume) indicated increased volume loss on active treatment and greater mean body weight loss was observed at 26 weeks on both doses vs control group.

In this communication, randomized participants were instructed to stop the study medication immediately (with confirmation of the last dose taken to be documented), and to return to the site to complete:

1. Modified Treatment Epoch Completion (TEC) visit 299 (mTEC).
 - The following assessments were no longer required: MRI, PET and Lumbar Puncture for CSF samples.
2. Modified End of Study visit 301 (mEOS):
 - Timing was changed from 3 month post Treatment Epoch Completion visit to 6 month post Treatment Epoch Completion visit:
 - Simplified assessments required at this visit included: AEs and SAEs, RBANS, CDR-SOB, volumetric MRI (3DT1 sequence only), blood sample for biomarkers.

The Follow-up #1 (1-Aug-2019) was issued as a clarification to the USM, to recommend that the full MRI scan and a lumbar puncture at mTEC visit be conducted as specified in protocol v02 in case of early study discontinuation. These assessments were expected to allow evaluation of potential markers associated with cognitive decline and/or imaging findings.

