A non-stratified log-rank test will be conducted to compare estimates of the hazard functions of the treatment arms.

In order to understand the potential longitudinal difference in the rate of disease progression by genotype, a longitudinal Cox PH model will be implemented as an important primary supportive analysis. This will be done by including the additional interaction term treatment arm × genotype × visit window.

Excluding data after discontinuation of study drug in APCC

As with the primary analysis method (MMRM) for APCC, this analysis will assume missing data to be MAR.

Within this analysis, the following data will be excluded (regarded as missing though it is available) and thus implicitly assumed to be MAR:

- Data retrieved from participants remaining in the treatment epoch beyond 12 weeks after permanent study drug discontinuation
- For intermediate study drug interruptions lasting longer than 12 weeks, off-drug APCC data during this period, but beyond the abovementioned 12 weeks. Assessments subsequent to resuming drug administration will be included in the analysis.

In addition to this analysis, the same tipping point, controlled imputation and ‘copy reference’ sensitivity analyses as planned for the primary analysis will be conducted, but additionally excluding the off-treatment data to be missing as mentioned above.

Other analyses on the endpoint APCC

The primary analysis of the APCC test score will be supported by the following important primary supportive analysis: An MMRM is based on the same assumptions as the primary analysis model and includes the same factors, but also including the additional interactions (and underlying factors)

- baseline hippocampal volume | visit window
- genotype (HM, HT) | visit window | treatment

The primary analysis will be supported by an MMRM similar to the primary model, but using time as a continuous factor. The interpretation of results from the primary analysis will also be supported by the investigation of change in treatment effects over distinct time periods.

Potential drug-drug-interaction (DDI)

Potential PD-mediated DDIs with frequent concomitant medications may include the use of cholinesterase inhibitors in terms of transient interaction with cognitive readouts.

Treatment interaction with CNP520 will be assessed as follows:

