For the RBANS total score, RBANS index scores and APCC score, effect sizes of change from baseline as well as 80% confidence intervals (CIs) for the effect size will be reported. The effect size (and CI) of change from baseline will be calculated for following post-baseline visits: Week 13 and Week 26, Week 52, TEC, EoS, last assessment on treatment, and last assessment off treatment. The effect size will follow the *Cohen’s d* formula: The raw mean to standard deviation ratio, not model based mean to standard deviation ratio. The effect size will be calculated as the difference between active and placebo in mean change from baseline divided by the pooled standard deviation of the change. Effect sizes and CIs will be calculated (active versus placebo, i.e. the two active CNP520 dose arms will be pooled together without stratification).

Derivation of study specific effect size *d* and corresponding CI

BL = Baseline value; PBL= Post baseline value;

SD = Standard deviation; SE = Standard error; n_1 = Sample size group 1; n_2 sample size group 2; S_1^2 = Variance group 1; S_2^2 = Variance group 2

Numerator: Mean change from BL to PBL active – mean change from BL to PBL control

Denominator: pooled SD defined as

$$SD_{pooled} = \sqrt{\frac{(n_1 - 1)S_1^2 + (n_2 - 1)S_2^2}{n_1 + n_2 - 2}}$$

Where the groups are given by factor treatment (active versus control).

The confidence interval can be derived using the formula proposed by [Hunter and Schmidt 2004](#) and [Nakagawa and Cuthill \(2007\)](#):

$$CI : d \pm z * SE(d)$$

Where z is the 10% Quantile of the normal distribution in case of the 80% CI. The SE(d) is calculated as

$$SE_d = \sqrt{\frac{(n_1 + n_2 - 1)}{(n_1 + n_2 - 3)} \left[\left(\frac{4}{n_1 + n_2} \right) \left(1 + \frac{d^2}{8} \right) \right]}$$

For CDR-SOB, corresponding confidence intervals for the difference between treatment groups will be provided.

Correlation between changes in RBANS total, APCC score and whole brain, hippocampal volume will be reported (correlation coefficient and R square will be reported by treatment group and visit (including also the last assessment on treatment, last assessment off treatment)).

Figures

Graphical presentation (forest plots) of the effect sizes and corresponding confidence intervals for RBANS total, RBANS index scores and APCC score by visit including TEC and EoS, as well as last assessment on treatment and last assessment off treatment.

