2.5.2 Volumetric MRI

Screening (baseline) volumetric measurements are performed using FreeSurfer software. This leads to reference volumes for whole brain, ventricles, hippocampus, and intra-cranial.

Volumetric data will be available for the following regions:

- intra-cranial volume (ICV),
- total/whole brain,
- left/right hippocampus,
- lateral ventricles.

In order to assess atrophy rate, volumetric MRI images from follow-up timepoints are compared to those from screening, using the boundary shift integral (BSI) technique in selected brain regions. The technique determines the total volume through which the boundaries of a given cerebral structure have moved, and hence, it aims at quantifying the amount of change in these selected brain regions. The output of the method is a change from baseline in volume (atrophy).

Volume changes in the following regions of interest (ROI) will be reported:

- whole brain,
- hippocampus (sum of left and right),
- lateral ventricles (left and right).

Tables

Summary statistics for absolute change and percent change from Baseline to timepoint will be provided. All statistics will be based on the total volume, i.e. the sum of the respective left and right volumes as applicable. In addition, the annualized percentage change will be calculated as the mean of individual participant annualized percentage change (percentage change per participant / time interval (in days) between current MRI assessment and date of baseline MRI assessment per participant) x 365.25. Time interval (in days) will be derived as date of current MRI assessment – date of baseline MRI assessment + 1.

Raw volumes, as well as changes, % changes, and annualized % changes from baseline will be summarized by visit including TEC, EoS, and last assessment on treatment, last assessment off treatment.

For investigation of worsening (increased atrophy) under treatment and reversibility, these summary statistics will also be provided for the mSAF by visit including TEC, EoS, and last assessment on treatment, last assessment off treatment.

The relationship between percentage change from baseline in hippocampal and whole brain volumes and change in RBANS total score and APCC score will be examined through correlation analysis. This will be done for participants with at least 3 months exposure (mSAF). The Spearman and Pearson correlation coefficients and associated p-values will be reported.

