2.5.4 Statistical hypothesis, model, and method of analysis

Except from the primary objective on the TTE endpoint, the other primary objective (for APCC) aimed to evaluate effects of CNP520 versus Placebo by comparing changes from baseline to Month 60. Due to the early termination of CNP520, no data have been collected at Month 60. Only very few participants have provided data on active treatment with CNP520 beyond one year of follow-up. Hence, the originally planned inferential and model based statistical analyses cannot be performed and are no longer applicable.

Time to event (MCI due to AD or dementia due to AD), Time to first change in diagnosis classification and Time to first decrease in RBANS Total of ≥ 14 points

Tables

Time to Event analysis using Kaplan Meier approach will be presented for time to MCI due to AD or Dementia due to AD (events as per protocol) and for time to first change in diagnosis classification (this is an event regardless of confirmation and adjudication) from cognitively unimpaired by the investigator. Analysis of time to first change in diagnosis classification will also be performed for participants on treatment. In addition, analysis of time to first decrease in RBANS Total Score of ≥ 14 points will be performed for participants on treatment (for on treatment definition, refer [Section 2.1.1](#)). The Kaplan-Meier estimates of the cumulative event rate for each treatment group will be summarized and plotted. To calculate the proportion of participants with events, number of participants at risk will be used as the denominator. "Participant at risk" at a specific time point is defined as the number of participants in the study without an event at up to that time point.

These analyses will only be performed if there are at least five such events.

In addition, the number and percentage of the additional situations ([Section 2.5.3](#)) defined events overall (not by visit) will be summarized by treatment group.

APCC score

Tables

The APCC test score and the seven components (listed above in [Section 2.5.3](#)) will be summarized on the SAF.

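### The SAP specifies no active-versus-placebo estimate with a confidence interval for time to event, brain volume or body weight, although it does for RBANS, APCC and CDR-SOB

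*SAP*

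**What the plan says.** - **Time to event (SAP 2.5.4, 5.4.1).** There are three outcomes: confirmed MCI or dementia due to AD, first investigator change in diagnosis classification, and first RBANS Total fall of 14 points or more. The plan is per arm: "The Kaplan-Meier estimates of the cumulative event rate for each treatment group will be summarized and plotted". It adds "Median time to event and quartiles including 95% confidence intervals, if estimable, will be provided for each treatment group using the SAS procedure LIFETEST", and per-arm cumulative event probabilities with 95% intervals. An output is produced only if there are at least five events.
- **Volumetric MRI (SAP 2.5.2).** Raw volume, change, percent change and annualised percent change are summarised by arm, with correlations against RBANS and APCC. The purpose is stated: "For investigation of worsening (increased atrophy) under treatment and reversibility, these summary statistics will also be provided for the mSAF". Under SAP 2.1 a continuous summary is n, mean, SD, median, minimum and maximum, so it has no interval.
- **Body weight (SAP 2.8.4.2).** Change from baseline by visit, and counts of notable changes, by arm.
- **Where a contrast is given (SAP 2.5.1).** RBANS and APCC get a pooled active-versus-placebo effect size with an 80% interval. For the key secondary scale, "For CDR-SOB, corresponding confidence intervals for the difference between treatment groups will be provided".
- **What the protocol had.** Section 9.4.2 has a Cox model for confirmed MCI or dementia. Section 9.4.4 adds: "A non-stratified log-rank test will be conducted to compare estimates of the hazard functions of the treatment arms". SAP Section 4 lists the primary, sensitivity and supportive analyses as not performed because of the early stop.

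**The concern.** The Amendment 03 rationale in the protocol says that, besides the cognitive signal, "volumetric MRI (whole brain and hippocampal volume) indicated increased volume loss on active treatment and greater mean body weight loss was observed". It later says that imbalances in brain volume and weight were still present after washout. How large these differences from placebo are, and how precisely they are known, is what a reader of the abbreviated report will ask. For cognition scores the SAP answers with an estimate and an interval. For brain volume and weight it gives columns to be compared by eye. For time to event it gives separate curves and separate intervals, and the section that provides for a pooled active column (SAP 2) exempts events and time to event. A reader left with separate intervals may take overlap to mean no difference, which is a much stricter standard than a direct comparison.

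**Working it through.** **1. Is a contrast specified in the SAP text?**

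| Output | Pooled active summary | Between-group estimate | Interval for it |
|---|---|---|---|
| RBANS, APCC (2.5.1) | yes | effect size | 80% |
| CDR-SOB (2.5.1) | yes | difference | yes, level not stated |
| Brain volume (2.5.2) | yes (Section 2) | none | none |
| Body weight (2.8.4.2) | yes (Section 2) | none | none |
| Time to event (2.5.4, 5.4.1) | not specified | none | none |

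The only between-arm tests in the SAP concern baseline comparability (2.3.3).

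**2. Do the stated reasons cover the gap?**

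- *No Month 60 data (SAP 2, 2.5.4).* Brain MRI was scheduled at Weeks 26 and 52 (protocol Table 6-1; SAP Table 5-16), and weight is windowed at both visits (SAP Table 5-14). SAP 2.5.4 itself separates the time-to-event objective from those defined at Month 60.
- *Few events (SAP 2.5.3).* This is said of confirmed MCI or dementia. Unconfirmed diagnosis change and the RBANS fall are broader outcomes, and the SAP plans curves for them.
- *Few participants on active drug beyond one year (SAP 2.5.4).* This limits late visits, not Weeks 26 and 52.

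**3. The plan's own design figure.** Inputs from SAP Section 3: "An alpha of 4% will be chosen to test the hypothesis" on time to diagnosis; "a hazard ratio of 0.75 in favor of the active treatment arm"; 80% power; 408 events for 50 mg versus placebo at 1:1.

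- Schoenfeld: 4(2.054 + 0.842)² / (ln 0.75)² = 4 × 8.383 / 0.0828, giving 406 events.
- Freedman: 8.383 × (1.75/0.25)² = 8.383 × 49, giving 411 events.

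The stated 408 lies between them, so the design figure reproduces.

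**4. What reading separate 95% intervals would cost, as a general illustration.** Two intervals fail to overlap only if the difference exceeds 1.96(se₁ + se₂). In units of the standard error of the difference, the critical value is 1.96k, where k = (se₁ + se₂)/√(se₁² + se₂²). Precision is taken as proportional to allocation. Power is Φ(z₁₋α/₂ + 0.842 − 1.96k), where α is the two-sided level at which the direct test has 80% power.

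| Allocation | k | 1.96k | α = 5% | α = 4% |
|---|---|---|---|---|
| 1:1 | 1.414 | 2.772 | 51.2% | 54.9% |
| 3:2 | 1.407 | 2.758 | 51.7% | 55.5% |
| 1:2 | 1.394 | 2.732 | 52.8% | 56.5% |

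The overlap rule is a test at a two-sided level of about 0.6%. This applies to time to event only, because the MRI and weight summaries have no intervals to compare.

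**5. How precise an added hazard ratio would be.** Event counts are assumed; the documents give none. For pooled active versus placebo at 3:2, SE(log HR) ≈ √(1/(0.6 × 0.4 × E)), and the 95% interval is the estimate divided and multiplied by exp(1.96 SE).

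- E = 5 (the SAP's floor): SE 0.913, factor 6.0
- E = 20: SE 0.456, factor 2.4
- E = 50: SE 0.289, factor 1.8
- E = 100: SE 0.204, factor 1.5

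No such figure can be given for brain volume or weight, because the documents give no SDs.

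**The case against.** The strongest reply is that this is an abbreviated report of a stopped trial and that the reduction is disclosed and reasoned (SAP 1, 2, 2.5.4 and 4). That stands: nothing is hidden.

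Three further points also stand.

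- The cognitive signal that triggered the stop does get a contrast.
- For brain volume and weight a reader can work out an unadjusted difference and interval from n, mean and SD. What is missing is a reported, baseline-adjusted estimate, not the information.
- The protocol's Cox model and log-rank test concerned confirmed MCI or dementia. Diagnosis change and the RBANS fall were not protocol endpoints, and the RBANS and on-treatment versions were added after database lock. No protocol contrast was removed from them.

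Two readings go further than the documents allow.

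- A reader might infer that the arms are never compared on these outcomes. The table shells and programming specifications are not supplied, and raw procedure output for all time-to-event analyses goes to CSR Appendix 16.1.9 (SAP 5.4.2). Only the SAP text can be judged. The exemption of time to event from the pooled column could also mean only that a by-visit format does not suit it.
- A reader might infer that this trial's power drops from 80% to about half. The SAP states no overlap rule, and no comparison with 80% power can be shown to survive the stop.

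The reply does not explain why scores get an interval for the difference while brain volume, whose stated purpose is to look for worsening under treatment, does not.

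**Conclusion.** The gap holds on the SAP text for time to event, volumetric MRI and change in body weight. It is inconsistent with SAP 2.5.1, so a descriptive-only policy cannot explain it, and the missing Month 60 data do not cover it. It is a reporting gap that should be closed; it is neither a concealed change nor a loss of data.

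Its numerical size in this trial cannot be stated without event counts and SDs. The fall from 80% to about 51–53% at a 5% level (about 55–56% at the trial's 4%) shows why separate intervals are a poor substitute for a contrast. It is not a realised loss here. For confirmed MCI or dementia an added interval will be wide, and printing it would show that plainly.

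**What to change.** **SAP 2.5.2.** Add the active-minus-placebo difference in mean percent change in whole-brain, hippocampal and lateral ventricular volume at Weeks 26 and 52 and at last on treatment. Give a 95% interval from ANCOVA with baseline volume and the randomisation factors (age group, region, genotype, and amyloid method within heterozygotes).

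**SAP 2.8.4.2.** Do the same for percent change in body weight, with baseline weight as covariate.

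**SAP 2.5.4 and 5.4.1.** For each time-to-event output that meets the existing five-event rule, add a pooled active curve and an active-versus-placebo hazard ratio with 95% interval. Use a Cox model with treatment as the only term, fixed in advance for every output. If the ratio cannot be estimated, say so and do not change the model. A multi-covariate model is not sensible with as few as five events.

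Label all of these descriptive, post hoc and unadjusted for multiplicity, and print the interval level, since 2.5.1 uses 80%.

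**Cost.** A few sentences and some added table rows, with no new data. The SAP's document history shows that post-lock addenda already added APCC effect sizes with intervals and the on-treatment time-to-event outputs. The price is wide intervals where events are few and a small amount of extra analysis.
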